9. ECONOMIC EVALUATION

9.1 Economic evaluation feasibility study

The feasibility economic evaluation will determine the feasibility of identifying, measuring and valuing the relevant resource use and quality of life data required to conduct the full cost-effectiveness/cost-consequences analysis in the definitive study. Key cost drivers will be identified within this feasibility study using data gathered from a specially designed resource use questionnaire as well as from an intervention costing exercise (identifying and measuring all aspects of resources used to deliver the intervention). All health care, personal social service (PSS) resource, employment data, and personal costs will be measured within this feasibility study. The questionnaire will be tailored to the resource use requirements of this population with multiple LTCs (informed by WP1 resource use analysis). Incorporation of the full spectrum of outcomes beyond the QALY (EQ-5D) within a feasibility cost-consequences analysis framework will further provide initial insights to such a pragmatic economic evaluation for this population with multiple LTCs.

9.2 Economic analysis of workforce impacts

This feasibility economic evaluation component will also provide an opportunity to inform broader workforce impacts and other service configuration resources required to deliver the PERFORM intervention (facilities, equipment) identified during the intervention development stage.

9.3 Health Economics Analysis Plan (HEAP)

Based on the feasibility study findings, a Health Economics Analysis Plan (HEAP) covering the economic analysis of the definitive within-study and cohort study will be developed and agreed with Programme Management Group and PSC/DMEC. The HEAP will describe in detail the economic evaluation comprising the following components:1) Economic evaluation alongside RCT; 2) Economic evaluation alongside a prospective cohort study (PCS); 3) Exploration of PERFORM workforce impacts and 4) Long-term economic modelling beyond RCT/PCS.

10. DATA ANALYSIS

10.1 Sample size calculation

In order to achieve the feasibility objectives (see above) of this feasibility study, a total of 60 patients will be recruited over 4.5 months. Given we are interested in the acceptability of the intervention, for efficiency, we will randomise 40 participants to the intervention group and 20 to the control group. We anticipate a loss to follow up of 20% at 3-months.

10.2 Statistical analysis plan

Aim: to be fully describe in the detailed statistical analysis plan (SAP).

10.2.1 Summary of baseline data and flow of patients

A CONSORT diagram showing the flow of participants through the study will be produced, including the number of patients screened, randomised and (in the intervention arm) receiving treatment. This diagram will also show the number of randomised patients providing complete EQ-5D data at 3 months (our proposed RCT primary patient outcome).

- Baseline characteristics and measures of the participants will be summarised by randomisation group and overall using mean (standard deviation) and median (interquartile range) for continuous variables and count (percentage) for categorical variables. There will be no tests of statistical significance nor confidence intervals for differences between randomised groups on any baseline variable.
- The number (percentage) of participants in each analysis population will be tabulated overall and by randomised group. The type and number (percentage) of protocol deviations will also be tabulated overall and by randomised group in the ITT population.

10.2.2 Co-Primary outcomes analysis

The number recruited and the percentage of the 60 patient recruitment target will be reported and recruitment rate per site reported.

The number and percentage (along with a 95% confidence interval) retained at 3 months, defined as having complete EQ-5D data at 3 months follow up, will be calculated for all patients randomised (ITT population).

The number and percentage (along with a 95% confidence interval) of patients randomised to the PERFORM intervention that attended ≥60% of sessions will be reported. In addition, the percentage of sessions attended by individuals in the PERFORM intervention arm will be summarised using median and inter-quartile range.

10.2.3 Secondary outcome analysis

The number and proportion of patients randomised with complete data for each of the follow-up outcomes (possible outcomes for the subsequent definitive trial) measured at 3 months follow up will be calculated in all randomised patients and by randomised group.

Patient reported outcomes at 3 months follow up and the number of each of the clinical events within 3 months follow up will be summarised by randomised group and overall using mean (standard deviation) and median (interquartile range) for continuous variables and count (percentage) for categorical variables. Intervention-control between group mean differences and 95% CIs will be reported. Given the feasibility objectives of the study, no P-values will be reported.

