2.4 Defintion of other feasibility outcomes

2.4.1 Feasibility and acceptability of data collection tools: will be measured by proportion of patients randomised with complete patient-related outcome data at 3 months follow up.

The following proposed patient outcomes will be collected at baseline (pre-randomisation) and 3 months follow up (post randomisation)*:

- HRQoL: EuroQoL (EQ-5D-5L)
- Exercise/functional capacity: incremental shuttle walk test (ISWT);
- 4 Metre Gait Speed (MGS)
- Strength: Hand Grip Strength
- Mood: Patient Health Questionnaire-9 (PHQ-9);

PERFORM FEASIBILITY Protocol

Version 2.0 16.MAY.2023

- Generalised Anxiety Disorder Assessment-7 (GAD-7)
- Physical activity: International Physical Activity Questionnaire (IPAQ)
- Frailty: Functional Assessment of Chronic Illness Therapy; Fried Exhaustion and Weight Loss
- Fatigue (FACIT-F)
- Pain: Brief Pain Inventory (BPI)
- Health and disability: WHODAS
- Breathlessness: Dyspnoea-12
- Sleep: Medical Outcome Study Sleep Scale (MOS Sleep Scale)
- Cognition: MoCA
- Multimorbidity Treatment Burden Questionnaire (MTBQ)
- ICEpop CAPability Measures for Adults (ICECAP-A)
- Clinical events mortality & hospital admissions (& primary care contacts); and social and healthcare utilisation (including medication (assess at follow up only))

The following proposed patient outcome will only be collected at 3 months follow up (post randomisation)*:

Exercise adherence: Exercise Adherence Rating Scale (EARS)

*This list of patient outcomes will be finalised following stakeholder consultation that forms part of WP2 and any changes will be submitted as an ethics amendment.

2.4.2 Estimates of key cost drivers.

Details are provided in the economic evaluation section (section 9).

2.4.3 Risks of bias/contamination.

Any outcome assessor blind breaks will be recorded. Contamination will be assessed by asking control participants to report whether they knew anyone in the intervention arm of the trial and whether they had access to any intervention resources.

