6.6 Randomisation

The LCTU will supply a web based randomisation system from a third party (Sealed Envelope Ltd.). Participants will be individually randomised in a 2:1 ratio to intervention or control. Once the participant has provided written consent to the study and a healthcare professional has confirmed eligibility, randomisation will be performed randomly allocated in a 2:1 ratio to either PERFORM rehabilitation programme or standard of care. Randomisation will be minimised on site. To maintain concealment and minimise selection bias, randomisation will be performed after the baseline visit using a valuated password-protected web-based randomisation system supported by Leicester CTU to ensure concealment.

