10.4 Adjusted analysis

Not applicable.

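### The 3-month between-group differences are planned unadjusted although baseline values and site are to hand; the estimates are valid, but adjustment would probably make them more precise (minor)

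*Protocol*

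**What the plan says.** - **Estimate.** Protocol 10.2.3 summarises the 3-month outcomes by group and adds: "Intervention-control between group mean differences and 95% CIs will be reported". It continues: "Given the feasibility objectives of the study, no P-values will be reported".
- **Adjustment.** The whole content of section 10.4, headed Adjusted analysis, is "Not applicable". This is a stated choice and not a detail left to the SAP; an SAP that adjusted would depart from the protocol.
- **Baseline data.** Section 2.4.1 introduces its main outcome list with "The following proposed patient outcomes will be collected at baseline (pre-randomisation) and 3 months follow up (post randomisation". The exceptions are the Exercise Adherence Rating Scale (EARS), placed at 3 months only, and the event and utilisation data marked for follow-up only.
- **Allocation.** Section 6.6: "Randomisation will be minimised on site". No other factor is named, so no baseline outcome is balanced by design.
- **Numbers.** Section 10.1 plans 40 intervention and 20 control participants and expects 20% loss at 3 months. Section 10.6 analyses patient outcomes in complete cases, variable by variable.

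**The concern.** Having decided to publish effect estimates with intervals, the plan leaves unused two pieces of information it will already hold: each participant's starting value on the same measure, and the site on which allocation was minimised.

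The arms are small and unequal, so sizeable baseline differences will arise by chance on some of the many outcomes listed. Section 10.2.1 would display them, but no estimate would take them into account.

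What is at stake is how useful the estimates are for planning the full trial. The outcomes are candidates for that trial, and section 10.2.1 names EQ-5D as its proposed primary patient outcome.

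**Working it through.** The protocol states no precision or effect size for these differences, so there is no figure of its own to reproduce. Everything below is in units of the outcome's SD.

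**Inputs**
- Randomised: 40 v 20 (section 10.1).
- Analysed after 20% loss: 40 × 0.8 = 32 and 20 × 0.8 = 16, total 48.
- Sites: four (sections 3 and 4; section 2.1.1 says three). Four is used here.
- Correlation r between baseline and 3-month value: not in the protocol. Assumed 0.3, 0.5 and 0.7.

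**Step 1. Unadjusted interval, as planned**
- SE = √(1/32 + 1/16) = 0.306.
- Degrees of freedom 48 − 2 = 46, t = 2.013.
- Half-width = 2.013 × 0.306 = 0.62.

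**Step 2. Interval adjusted for baseline and site**
- Degrees of freedom 48 − 2 − 1 (baseline) − 3 (site) = 42, t = 2.018.
- Half-width ≈ 2.018 × 0.306 × √(1 − r²). This leaves out the small loss from chance covariate imbalance and gives site no explanatory value.
- Simulation of the same model adds that loss. With sites balanced across arms among those analysed, it returns 0.59, 0.54 and 0.44 for the three correlations, the same as the formula. With sites left to fall at random, it gives the wider values below.

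| Assumed r | Formula | Simulated, sites unbalanced | Change from the simulated unadjusted 0.61 |
|---|---|---|---|
| 0.3 | 0.59 | 0.61 | none |
| 0.5 | 0.54 | 0.56 | 9% narrower |
| 0.7 | 0.44 | 0.46 | 25% narrower |

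**Step 3. Chance baseline imbalance**
- Among those analysed, the baseline difference between arms has SD √(1/32 + 1/16) = 0.306, about 0.31.
- For any one outcome, the probability that it exceeds 0.3 SD in either direction is about 33% (0.3/0.306 = 0.98). For 0.5 SD it is about 10% (0.5/0.306 = 1.63).
- Only a share r carries into the 3-month difference. The carried-over part has SD r × 0.306: 0.09 at r = 0.3, 0.15 at r = 0.5 and 0.21 at r = 0.7.

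**The case against.** The strongest reply is that nothing here is in error. Over repeated randomisations an unadjusted difference is unbiased, and its interval already includes the variability due to chance baseline imbalance. Simple descriptive differences without P-values are a defensible choice in a 60-patient feasibility study. This stands: the point concerns efficiency.

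Four stronger readings are tempting, and the documents do not support them.

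- **That the go/no-go decision is affected.** Sections 2.2 and 2.3 base progression on recruitment, retention and attendance. EQ-5D enters only as completeness of data, never as a treatment difference.
- **That a baseline imbalance passes whole into the result.** Only the share r does.
- **That leaving out the minimisation factor makes the interval too narrow.** When site is balanced and outcomes differ between sites, ignoring it tends to make the interval too wide. The protocol gives no between-site variation, so no size can be put on this.
- **That a large gain is assured.** It depends on a correlation the protocol does not give, and one that may differ widely between, say, grip strength and a 7-day activity recall. At 0.3 there is little or none.

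It can also be said that baseline summaries by arm let readers see an imbalance for themselves. That is true, but seeing it does not give an estimate that allows for it. Finally, because the analysis is in complete cases, adjustment could also reduce bias if loss depended on baseline health and differed by arm. Nothing in the protocol shows that it will, so the point does not rest on this.

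**Conclusion.** The point holds as a minor improvement in efficiency. The planned estimates are valid, but they set aside baseline values that will already have been collected.

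At 32 v 16, the 95% half-width of about 0.62 SD would become about 0.59–0.61 at r = 0.3, 0.54–0.56 at r = 0.5 and 0.44–0.46 at r = 0.7. In each range the lower figure assumes sites balanced across arms among those analysed, and the upper figure does not. Adjustment would also allow for the part of a chance baseline imbalance (SD about 0.31) that otherwise carries over.

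These figures rest on the protocol's 20% loss falling equally on both arms, four sites, no between-site differences in outcome, and assumed correlations. That sections 10.2.3 and 10.4 plan unadjusted estimates is certain. The size of the gain is not.

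**What to change.** Replace the entry in section 10.4, and align section 10.2.3 with it, as follows:

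- Estimate each continuous outcome's between-group difference by linear regression on randomised group, baseline value of the same outcome (where collected) and site, with a 95% CI and no P-value.
- Adjust EARS for site only, since section 2.4.1 gives it no baseline value.
- Keep the raw summaries by group alongside.
- For EQ-5D, report the residual SD and the baseline/follow-up correlation to inform the full trial.

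The cost is a protocol wording change, matching SAP text and a few lines of code, with no new data, visits or participants. The statistical price is about 4 degrees of freedom (one for baseline, three for four sites). For outcomes with a low baseline/follow-up correlation, the interval may be no narrower than the unadjusted one.

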10.3 Subgroup analyses

Not applicable.

10.4 Adjusted analysis

Not applicable.

10.5 Interim analysis and criteria for the premature termination of the study

There are no formal criteria for stopping the study prematurely.

No interim analysis assessing the feasibility stop-go criteria with the possibility of early termination of the study is planned. However, due to the nature of the outcomes of recruitment and retention, these outcomes will be monitored along with serious adverse events throughout the study.

10.6 Participant population

The analysis of the feasibility outcomes will be carried out in the ITT population.

Patient reported outcomes and clinical events will be analysed using the complete case population for the variable being summarised.

Adverse events will be analysed in the safety population, that all individual randomised with individuals receiving one or more session of the PERFORM intervention being analysed in the PERFORM intervention arm.

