For this study, only SAEs deemed related to the PERFORM rehabilitation programme (intervention) or study assessments

| Version 2.0 10.IVIA1.2025 | will be reported and reviewed by the PSC and Sponsor. SAEs will be reviewed by the site PI to determine relatedness. |
|---|--|
| Serious Adverse Reaction (SAR) | An adverse event that is both serious and, in the opinion of the reporting Investigator, believed with reasonable probability to be due to one of the trial treatments, based on the information provided. |
| | For this study, only SAEs deemed related to the PERFORM rehabilitation programme (intervention) or study assessments will be reported and reviewed by the PSC and Sponsor. SAEs will be reviewed by the site PI to determine relatedness. |
| Expected Serious Adverse Events/Reactions | Only related SAE/SARs will be reported for the PERFORM feasibility study due to the nature of the patient population and feasibility aspect of this study. There are no expected serious adverse events/reactions, however due to the exercise nature of the PERFORM rehabilitation programme and assessments, injuries such as musculoskeletal injuries, etc. may be deemed related and 'expected' as such. These will be evaluated on a case-by-case scenario and will be decided by PI and/or CI. |
| Suspected Unexpected Serious Adverse Reaction | A serious adverse reaction, the nature and severity of which is not consistent with the information about the medicinal product in question set out in the reference safety information: |
| (SUSAR) | in the case of a product with a marketing authorisation, this could be in the summary of product characteristics (SmPC) for that product, so long as it is being used within it's licence. If it is being used off label an assessment of the SmPCs suitability will need to be undertaken. in the case of any other investigational medicinal product, in the investigator's brochure (IB) relating to the trial in question |

NB: to avoid confusion or misunderstanding of the difference between the terms "serious" and "severe", the following note of clarification is provided: "Severe" is often used to describe intensity of a specific event, which may be of relatively minor medical significance. "Seriousness" is the regulatory definition supplied above.

Detailed guidance can be found here:

http://ec.europa.eu/health/files/eudralex/vol-10/2011 c172 01/2011 c172 01 en.pdf

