6.13.1 Reporting Procedures for Serious Adverse Events

All SAEs related to the PERFORM study or rehabilitation programme (intervention) occurring from the time of written informed consent until the 3 month follow up visit must be reported to the Sponsor immediately and within 24 hours of becoming aware of the event. These related SAEs will be reported using appropriate forms and according to the Sponsor SOP for reporting serious adverse events. Additional information will be provided if requested to the Sponsor and main Research Ethics Committee (REC). The Principal Investigator or another delegated physician (as agreed by the Sponsor) is responsible for

the review and sign off of the SAE and the assessment of causality (i.e. whether an event is related to a study procedure or intervention).

If a delegated clinican from the reporting site is unavailable at the time of identification of a SAE the initial report without assessment of whether the event was related to the study or intervention should be submitted to the Sponsor. This must be completed immediately and within 24 hours of the study team becoming aware of the SAE, and must be followed-up by medical assessment as soon as possible thereafter.

The Sponsor will perform an initial check of the information and ensure that the SAE line listing is reviewed by the Director of Research & Innovation. All SAE information must be recorded on an SAE form and sent to the Sponsor. Additional information received for a case (follow-up or corrections to the original case) needs to be detailed on a new SAE form and sent to the Sponsor.

Copies of all documentation and correspondence relating to SAEs will be stored in the TMF and / or ISF

For each SAE the following information will be collected:

- a) full details in medical terms and case description
- b) event duration (start and end dates, if applicable)
- c) action taken
- d) outcome
- e) seriousness criteria
- f) relationship to the study procedure or intervention

Any change of condition or other follow-up information should be emailed to the Sponsor as soon as it is available or at least within 24 hours of the information becoming available. Events will be followed up until the event has resolved or a final outcome has been reached."

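### Section 10.6 gives deaths and hospital admissions the same complete-case rule as questionnaires, so events in patients who miss the 3-month visit may go uncounted

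*Protocol*

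**What the plan says.** Section 10.6 sets one rule for two kinds of data: "Patient reported outcomes and clinical events will be analysed using the complete case population for the variable being summarised". Section 2.4.1 shows what the second kind contains: "Clinical events mortality & hospital admissions (& primary care contacts); and social and healthcare utilisation (including medication (assess at follow up only". Section 10.2.3 then states that "the number of each of the clinical events within 3 months follow up will be summarised by randomised group and overall". Section 10.7 adds that a wholly missing outcome is not imputed.

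The schedule in section 6.1 places the follow-up assessments, the post-baseline outcome questionnaires and the resource-use questionnaire at a single visit, 3 months after randomisation with 4 weeks' leeway either side. Section 4 holds follow-up on NHS premises. On attrition, section 10.1 states: "We anticipate a loss to follow up of 20% at 3-months".

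On safety reporting, section 6.13 states: "Only related SAE/SARs will be reported for the PERFORM feasibility study due to the nature of the patient population and feasibility aspect of this study". Section 6.13.1 covers related SAEs "occurring from the time of written informed consent until the 3 month follow up visit must be reported to the Sponsor". The Programme Steering Committee paragraph in the front matter reads differently: its routine reports are to summarise every SAE, and fatal or life-threatening SAEs are to reach it as well as related ones.

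Section 11.1 names medical records as a source of data. The protocol does not say that they will be searched for patients who miss the visit.

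**The concern.** A complete-case rule is a reasonable choice for a questionnaire score in a descriptive feasibility study. An event count is different. A patient who has died cannot attend, and one who is in hospital or recovering may not, so having the event makes the record more likely to be missing. Dropping incomplete records then removes events selectively.

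SAE reporting would normally act as a second route. Here sections 6.13 and 6.13.1 confine it to events judged related to the programme or to study assessments. In people with several long-term conditions, many deaths and admissions may be judged unrelated.

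Chance knowledge of events may also differ by arm. Intervention patients meet staff at supervised sessions over 8 weeks and at a discharge appointment (section 7.1). Controls continue usual care alone (section 7.2), with no study contact scheduled between baseline and 3 months. Staff are more likely to hear of an event in the intervention arm.

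At stake are the event summaries by group and the hospital-use component of the cost drivers in section 9.1.

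**Working it through.** **Routes by which an unrelated death or admission in a non-attender could be counted**

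| Route | What the protocol says | Secure? |
|---|---|---|
| 3-month visit (6.1) | Follow-up outcomes and resource use collected here | No, the visit was missed |
| SAE report (6.13, 6.13.1) | Related events only | No |
| Steering Committee report (front matter) | All SAEs, including fatal ones | Unclear, conflicts with 6.13 and 6.13.1 |
| Medical records (11.1) | Named as source data | Possible, but no search is required |

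**Inputs.** From section 10.1: 60 randomised (40 intervention, 20 control) and 20% loss. The protocol gives no event rates, so those below are assumptions.

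**The plan's own figures.** 40 + 20 = 60. Expected loss is 0.20 × 60 = 12, leaving 48. If loss is equal by arm, that is 8 intervention and 4 control.

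**Formula.** Let p be the proportion with an event among the 48 attenders and k the ratio of risk in non-attenders to that in attenders. If no event in a non-attender is captured, the complete-case rate is p, and the rate in all randomised patients is (48p + 12kp)/60.

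At p = 5%:
- k = 1: (2.4 + 0.6)/60 = 5%
- k = 2: (2.4 + 1.2)/60 = 3.6/60 = 6%
- k = 3: (2.4 + 1.8)/60 = 4.2/60 = 7%

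Over a wider range of assumed p:

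| p (reported) | k = 1 | k = 2 | k = 3 |
|---|---|---|---|
| 2% | 2% | 2.4% | 2.8% |
| 5% | 5% | 6% | 7% |
| 10% | 10% | 12% | 14% |
| 15% | 15% | 18% | 21% |

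**Share of events falling among the 12.** This is 12k/(48 + 12k): 20% at k = 1, 33% at k = 2, 43% at k = 3.

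**Chance that at least one of the 12 has an event, at equal risk.** This is 1 − (1 − p)^12: 22% at p = 2%, 46% at 5% and 86% at 15%.

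At k = 1 the rate is not biased, although events are still lost from the count. Understatement of the rate needs k above 1, which is plausible for events that prevent attendance but is not shown by anything in the protocol.

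**The case against.** The strongest reply is that section 10.6 defines completeness variable by variable, not by attendance and not by a completed EQ-5D. A known death is a complete observation for mortality, and an admission found in the notes is complete for admissions. Nothing excludes a non-attender whose event is known. This stands, so a reader should not infer that the protocol drops these events; it only leaves their capture to chance. The same reading leaves the denominator loose. If known events in non-attenders count while the other non-attenders are left out as unknown, the k = 2 case above gives 3.6/(48 + 1.2) = 7.3% against a true 6%, an error in the other direction.

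A reader might also infer that an unrelated event in a non-attender is captured by neither route. The documents do not settle that. The Steering Committee text covers all SAEs, section 6.13 has the site PI judge relatedness, and section 10.8 has the listing show it, which would add little if only related events were listed. The contradiction is real, but a site following 6.13 and 6.13.1 would not send unrelated events to the Sponsor.

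Three further points stand. The 4-week leeway lets some inpatients attend after discharge. The 20% is loss to follow-up, and retention in section 2.3 means complete EQ-5D; neither is the proportion with unknown vital status or admissions. Progression rests on recruitment, retention and attendance alone.

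Finally, handling of non-attenders could be left to the SAP or the Data Management Plan, neither of which is at hand. That would answer a complaint of silence. The point here is that the protocol states a rule for clinical events, and the rule suits them poorly.

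**Conclusion.** The point holds in a limited form. Section 10.6 applies a rule suited to questionnaires to events that can themselves cause the missing visit, and related-only SAE reporting is not a dependable second route. Event rates may be understated, and possibly unevenly between arms. The protocol does not support saying that they are understated.

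The size cannot be fixed from the document. Under an assumed 5% in attenders and two to three times that in 12 non-attenders, the true rate is 6% to 7% against 5% reported, or about one to two patients in 60 (1.2 to 1.8 uncounted). This treats everyone lost to follow-up as having unknown event status, so for a given p and k it is an upper case.

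The consequence is modest. The affected tables are descriptive secondary summaries without P-values, together with inputs to the cost drivers. A reader might infer a threat to the go/no-go decision, but none of the progression criteria in section 2.2 uses deaths or admissions. The change is still worth making, because it is cheap and less open to bias than the stated rule.

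**What to change.** In section 10.6, separate clinical events from patient-reported outcomes and keep the complete-case rule for the latter. For deaths and hospital admissions:

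- seek vital status and admissions up to 3 months for every randomised patient, using medical records where the visit is missed;
- summarise by randomised group, with the number randomised as denominator;
- report the number with unknown status in each arm, so that the reader can see how far the count is a minimum.

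Separately, reconcile the Programme Steering Committee paragraph with sections 6.13 and 6.13.1 on which SAEs are reported.

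The cost is a notes check for about 12 patients, a short change to 10.6 and a matching line in the SAP. Primary-care contacts may remain incomplete for those patients. The check would also show whether ascertainment from records works, which is useful to know before the full trial.
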